2 STUDY OBJECTIVES AND ENDPOINTS

2.1 Primary Objective and Primary Endpoint

The main purpose of the study is to show that MMF in the initial treatment of SSNS in children is not inferior regarding maintenance of initial remission and subsequent relapse rate compared to the standard high-dose prednisone regimen.

The primary efficacy endpoint is occurrence of treated relapse within 24 months after completion of initial treatment (rationale: this endpoint was chosen in all previous studies on the initial treatment of SSNS in children and is also the primary endpoint in various meta-analyses on this topic [3,4,5,7,8]).

Relapses of the SSNS will primarily be detected by daily urine dip stick analysis (Albustix[®], PZN 1266154), which is performed and documented by the patients and parents themselves. Definition of relapse: Relapse is denoted by a reappearance of proteinuria for 3 consecutive days:

Albustix[®]≥2+ (first or second morning urine) (for interpretation see Albustix[®])

or

urine protein/creatinine (Up/c) ratio ≥2 g/g (first or second morning urine)

or

urine protein level of ≥40mg/m² BSA/h (urine collection for minimum 12 hours)

Relapses with and without treatment are documented. The primary endpoint is fulfilled by the first treated relapse.

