3.2 Study Duration and Schedule

The duration of the study for each subject is expected to be 27 months (including 24 months follow-up after intervention)

Study duration:

Total study duration: [78 months] Duration of clinical phase: [63 months] Beginning of the preparation phase: [03/2014] FSI (first subject in): [01/2015] LSI (last subject in): [01/2018] LSO (last subject out): [04/2020] DBL (database lock): [07/2020] Statistical analyses completed: [08/2020] Study report completed: [04/2021]

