5.4.2 Dosage Schedule

Maximum duration of treatment: 12 weeks after first day of initial treatment of SSNS. Patients will receive the whole medication for the complete intervention period.

Control intervention:

- The Prednisone, which is continued for a total of 6 weeks with the dosage of 60 mg/m² BSA/d (maximum 80 mg), is given once a day (quaque die (QD)), twice a day (bis in die (BID)) or three times daily (ter in die (TID)).
- The Prednisone, which is given for another total of 6 weeks with the dosage of 40 mg/m² BSA (maximum 60 mg) is given on alternate days (every other day) in one dose in the morning

Resorption of prednisone is independent of food intake.

Experimental intervention:

- Mycophenolate mofetil (MMF) is given in a dosage of 1200 mg/m² BSA/d as a suspension (200 mg/mL) until 12 weeks total treatment duration. MMF is given twice a day (bis in die (BID) = every 12 hours (± one hour).
- The suspension of MMF should be mixed in the study center (according to the Fachinformation).
- The persons having care and custody of the child are informed, that MMF should be given 30 minutes before or 60 minutes after food intake.
- For the first two weeks from randomization/visit1 on, prednisone is given with the dosage of 40 mg/m² BSA (maximum 60 mg) on alternate days (every other day) in one dose in the morning

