Second follow-up	Visit 5	9 months after day 1 (= first day of treatment with standard therapy)	± 14 days
Third follow-up	Visit 6	15 months after day 1 (= first day of treatment with standard therapy)	± 14 days
Fourth follow-up	Visit 7	21 months after day 1 (= first day of treatment with standard therapy)	± 14 days
End of study	Visit 8	27 months after day 1 (= first day of treatment with standard therapy)	± 14 days

^{*} In case the patient is randomized into the experimental intervention group at the fifth day after remission has been achieved start of mycophenolate mofetil is possible at the same day or the next day (i.e. day 6 after remission).

Visit 1

Visit 1 is scheduled at the point in time of allocation to the INTENT study and randomization (0-5 days after date of remission). The exact date depends on the time between first day of treatment with standard therapy for first episode of idiopathic nephrotic syndrome in children (= day 1) and the point in time of remission (this may vary between day 5 until day 28).

At visit 1 the history of the patient is documented: Age, gender, postal code (first 4 of 5 digits), known allergies, other chronic diseases, family history concerning kidney disease. Furthermore side effects of the previous standard treatment are retrieved in yes/no manner (Behavioral disturbances since diagnosis: child feels sad, anxious, irritable, as well as euphoric state, aggressive state, nausea, vomiting (defined as a frequency of more than 1 times per day), diarrhea (defined as a frequency of more than 4 loose stools daily), headache, muscle weakness, any new infection (e.g. respiratory tract infection, gastroenteritis, urinary tract infection)). Application of any current medication (other than immunosuppressive agents) is documented.

The physical examination contains investigation of the skin in yes/no manner (acne, cushingoid facies, striae, and hypertrichosis), further pathological organ-specific findings in yes/no/not done manner (lymphadenopathy, pharyngitis, otitis media, heart murmur, arrhythmia, respiratory tract infection, abdominal pain, and muscle weakness) and pubertal status.

Measurement of weight, height (BMI is computed) and blood pressure after 3 minutes rest are done and documented.

A sample of spot urine is analyzed with dip stick (Albustix®) and quantitatively for creatinine, protein, albumin in the laboratory of the study center (urine protein/creatinine ratio is computed).

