Visit 7 is scheduled at 21 months (± 14 days) after day 1 (= first day of treatment with standard therapy for first episode of idiopathic nephrotic syndrome in children).

At visit 7, the history since visit 6 is documented, especially if one or more relapses occurred since visit 6. In case of a relapse, date of first day of relapse (definition fulfilled) is documented. For each relapse, it is documented, according to which criteria the relapse was diagnosed: Albustix $\geq 2+$ (>30mg/dL) for 3 consecutive days, Spot urine: Up/c ratio ≥ 2 g/g, or collecting urine: Up excretion of ≥ 40 mg/m² BSA/h. If the relapse was treated, the medication is recorded. Further, date of remission is documented (see definitions). In order to document possible trigger factor infections during relapse (e.g. respiratory tract infection, gastroenteritis) and vaccinations within two weeks prior to the relapse are recorded, too. All information from the diary (days missing school attendance, days of hospitalization) since last visit are recorded.

Side effects of the treatment are retrieved in yes/no manner (Behavioral disturbances since visit 6: child feels sad, anxious, irritable, as well as euphoric state, aggressive state, nausea, vomiting (defined as a frequency of more than 1 times per day), diarrhea (defined as a frequency of more than 4 loose stools daily), headache, muscle weakness, any new infection).

Application of any current medication (other than immunosuppressive agents) is documented.

Application of further immunosuppressive agents since visit 6 are recorded.

The event of renal biopsy since last visit is recorded with histology.

The physical examination contains investigation of the skin in yes/no manner (acne, cushingoid facies, striae, and hypertrichosis), further pathological organ-specific findings in yes/no/not done manner (lymphadenopathy, pharyngitis, otitis media, heart murmur, arrhythmia, respiratory tract infection, abdominal pain, and muscle weakness) and pubertal status.

Measurement of weight, height (BMI is computed) and blood pressure after 3 minutes rest are done and documented.

A sample of spot urine is analyzed with dip stick (Albustix®) and quantitatively for creatinine, protein, albumin in the laboratory of the study center (urine protein/creatinine ratio is computed).

Visit 8 (end of study)

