Visit 8 is scheduled at 27 months (± 14 days) after day 1 (= first day of treatment with standard therapy for first episode of idiopathic nephrotic syndrome in children).

At visit 8, the history since last visit is documented, especially if one or more relapses occurred since visit 7. In case of a relapse, date of first day of relapse (definition fulfilled) is documented. For each relapse, it is documented, according to which criteria the relapse was diagnosed: Albustix $\geq 2+$ (>30mg/dL) for 3 consecutive days, Spot urine: Up/c ratio ≥ 2 g/g, or collecting urine: Up excretion of ≥ 40 mg/m² BSA/h. If the relapse was treated, the medication is recorded. Further, date of remission is documented (see definitions). In order to document possible trigger factor infections during relapse (e.g. respiratory tract infection, gastroenteritis) and vaccinations within two weeks prior to the relapse are recorded, too. All information from the diary (days missing school attendance, days of hospitalization) since last visit are recorded.

Side effects of the treatment are retrieved in yes/no manner (Behavioral disturbances since last visit: child feels sad, anxious, irritable, as well as euphoric state, aggressive state, nausea, vomiting (defined as a frequency of more than 1 times per day), diarrhea (defined as a frequency of more than 4 loose stools daily), headache, muscle weakness, any new infection).

Application of any current medication (other than immunosuppressive agents) is documented.

Application of further immunosuppressive agents since last visit are recorded.

The event of renal biopsy since last visit is recorded with histology.

The physical examination contains investigation of the skin in yes/no manner (acne, cushingoid facies, striae, and hypertrichosis), further pathological organ-specific findings in yes/no/not done manner (lymphadenopathy, pharyngitis, otitis media, heart murmur, arrhythmia, respiratory tract infection, abdominal pain, and muscle weakness) and pubertal status.

Measurement of weight, height (BMI is computed) and blood pressure after 3 minutes rest are done and documented.

A sample of spot urine is analyzed with dip stick (Albustix®) and quantitatively for creatinine, protein, albumin in the laboratory of the study center (urine protein/creatinine ratio is computed).

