	* If the results of Albustix™ are not clear, first or second morning urine or a specimen of a urine collection has to be checked. This can be performed at the study center or at any pediatrician. A spot urine sample with a protein/creatinine (Up/c) ratio of ≥ 2 g/g or a urine protein excretion of ≥ 40 mg/m² BSA/h (urine collection for a minimum of 12 hours) will define the relapse.	
	In case of a relapse the study center should be informed by the persons having care and custody of the child.	
	After diagnosis of a relapse, a time period of up to 10 days is allowed for a possible spontaneous remission, before standard therapy for relapse is initiated (see below). This decision is at the discretion of the study center. Treatment of the relapse has to be initiated according to the standard therapy of the GPN (see below).	
	Relapses with and without treatment are documented in the eCRF.	
Standard therapy for relapse of idiopathic nephrotic syndrome in children	Prednisone 60 mg/m ² BSA/d (maximum 80 mg) until remission (this dose is given in one dose or in two to three divided dosages per day with highest dosage in the morning), which is denoted by a reduction of urinary protein concentration or excretion in the first or second morning urine for 3 consecutive days to:	[4,8]
	Albustix [™] negative or trace or	
	$\frac{d}{Up/c} \le 0.2 \text{ g/g}^*$	
	or urine protein excretion of ≤ 4 mg/m² BSA/h (urine collection for a minimum of 12 hours)*	
	* If the results of Albustix™ are doubtful, first or second morning urine or a specimen of a urine collection has to be checked. This can be performed at the study center or at any pediatrician.	
	Followed by	
	Prednisone 40 mg/m ² BSA (maximum 60 mg) on alternate days for 4 weeks	

	(entire dosage is given in the morning)	
	(alternate day = every second day)	
Frequently relapsing nephrotic syndrome	Relapses occur 4 or more times in any 12 month period or 2 or more relapses within the first 6 months period after initial response.	[4,23,25]
Steroid-dependent nephrotic syndrome (SDNS)	Relapses occur during the alternate day prednisone treatment period or within 2 weeks after discontinuation of prednisone treatment.	[4,23,25]
Steroid-resistant nephrotic syndrome (SRNS)	No remission within 28 days after initiation of standard prednisone therapy for the first episode of idiopathic nephrotic syndrome in children	[4,23,25]
eGFR	Estimated glomerular filtration rate	[25,26]
	Formula = (K * height [cm])/serum creatinine [mg/dl]	

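### The 14-day early tolerance on visit 8 lets the last relapse assessment fall about 6 to 9 days before the 24-month primary endpoint window closes; a minor mismatch, cheap to align

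*Protocol*

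**What the plan says.** Section 2.1 defines the primary endpoint as "occurrence of treated relapse within 24 months after completion of initial treatment". Section 5.4.2 fixes when that clock starts: "Maximum duration of treatment: 12 weeks after first day of initial treatment of SSNS". Section 3.2 states the intended follow-up: "The duration of the study for each subject is expected to be 27 months (including 24 months follow-up after intervention".

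The final visit is anchored to day 1 and not to the end of treatment. The visit table in Section 6.1 puts it at "27 months after day 1 (= first day of treatment with standard therapy", and the visit text repeats this with the tolerance: "Visit 8 is scheduled at 27 months (± 14 days) after day 1". Its heading there is "Visit 8 (end of study". Relapses are recorded at visit 8 from the history and diary since the previous visit. After completion of the study, Section 6.1 leaves care to center practice.

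Only treated relapses count towards the endpoint. Appendix 1 says that after a relapse is diagnosed "a time period of up to 10 days is allowed for a possible spontaneous remission, before standard therapy for relapse is initiated".

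**The concern.** Two clocks run from different starting points and are assumed to agree. The endpoint clock runs for 24 months from the end of a 12-week treatment. The visit clock runs for 27 months from day 1. They would coincide if 12 weeks were three months, but 12 weeks is about a week shorter. The nominal visit 8 therefore has about a week to spare, while the tolerance allows it to be two weeks early.

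The primary test in Section 8.4 compares simple proportions, so each child without an event should be observed to the end of the window. A child seen early but within tolerance has complied fully, yet the last days of the primary outcome have not been observed. An analysis plan cannot recover days that nobody recorded.

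**Working it through.** **Inputs.** Treatment length 12 weeks = 84 days from day 1 (Section 5.4.2). Endpoint window 24 months (Section 2.1). Visit 8 at 27 months after day 1, ±14 days (Section 6.1). Relapse rate 51% in both arms, margin 0.15, one-sided 5%, power 80%, 136 per group (Section 8.1).

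**The plan's own sample size.** Farrington-Manning with restricted estimates 0.5846 and 0.4346:

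n = [(1.645 × √(0.5846×0.4154 + 0.4346×0.5654) + 0.842 × √(2×0.51×0.49)) / 0.15]² = 135.3, so 136 per group and 272 in total; 272/0.80 = 340. The stated figures are reproduced, and nothing below changes them.

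**Gap between the two clocks.** With an average month of 30.4375 days:

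- window closes: 84 + 24 × 30.4375 = day 814.5
- nominal visit 8: 27 × 30.4375 = day 821.8, or 7.3 days after closing
- earliest permitted visit 8: 821.8 − 14 = day 807.8, or 6.7 days before closing

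A calendar example: day 1 on 1 January 2015. Treatment ends on 26 March 2015 and the window closes on 26 March 2017. Nominal visit 8 is 1 April 2017 (6 days after closing). The earliest permitted visit is 18 March 2017 (8 days before closing).

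Over all 1,126 start dates from 01/2015 to 01/2018, the nominal visit is 5 to 8 days after closing. The gap at the earliest permitted visit is:

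| Gap (days) | 6 | 7 | 8 | 9 |
|---|---|---|---|---|
| Start dates | 634 | 250 | 184 | 58 |

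Mean = (634×6 + 250×7 + 184×8 + 58×9)/1,126 = 6.7 days. If day 84 itself is the last treatment day (day 1 + 83), the gap is 5 to 8 days, mean 5.7.

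**Share of visits before closing.** The protocol gives no distribution of visit dates, so this is a range under assumptions:

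| Assumed visit timing within ±14 days | Share before closing |
|---|---|
| Uniform over 29 days (6.7/29) | 23% on average; 21% to 31% by start date |
| Truncated normal, SD 10 days | 17% |
| Truncated normal, SD 7 days | 12% |
| Truncated normal, SD 5 days | 6% |
| Truncated normal, SD 3 days | under 1% |

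Under the day-84 convention the uniform share is 20%.

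**Effect on the relapse rate.** Assume a constant hazard giving 51% at 24 months: h = −ln(0.49)/730.5 = 0.000977 per day. Each lost day at the end of the window costs about 0.49 × 0.000977 = 0.048 percentage points.

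- Every child on the earliest day: 6.7 × 0.048 = 0.32 points, or 0.44 first relapses per 136 children.
- Uniform timing, mean loss 0.905 days over all visits: 0.905 × 0.048 = 0.04 points, or 0.06 per 136.

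**The case against.** The strongest reply is that the planned schedule works: at the nominal date the window is already closed, so the 24 months of Section 3.2 are delivered, and only early visits fall short. The loss is a small fraction of one relapse per arm under even timing, and both arms follow the same schedule. This stands, and it sets the weight of the point.

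It can also be said that data might still reach the database. The visit 8 special investigations may be done up to 28 days after the visit, the children stay in specialized centers, and three months separate last subject out from database lock. However, those investigations cover blood pressure, eyes, quality of life and the heart, not relapse. The routine-data route in Section 4.4.1 is only for children who leave the study. A late relapse check would be easy, but none is required.

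A reader might infer more than the protocol supports, in three ways:

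- **That about a quarter of relapse-free children leave too early.** This needs visit dates spread evenly over the 29 days, and nothing in the protocol supports that assumption.
- **That such children are formally missing, against the expectation in Section 8.4 of no missing primary outcomes in the per-protocol set.** The protocol does not class a child seen within the visit window as missing. How that visit maps to the 24-month outcome is a derivation rule that may properly sit in the analysis plan.
- **That over half of the permitted dates (about 57%) are too early, because treatment of a relapse may wait up to 10 days.** This holds only if onset, and not start of treatment, must lie inside the window, and the protocol does not say which. If start of treatment counts, a relapse first treated after closing is correctly not an event. The 10 days are also a maximum, at the center's discretion.

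**Conclusion.** The mismatch is real but minor. A fully compliant end-of-study visit can fall about 6 to 9 days before the primary endpoint window closes (5 to 8 days if day 84 is the last treatment day), with no later relapse assessment described. The share of relapse-free children affected cannot be known from the protocol.

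The numerical effect is at most about 0.3 percentage points, averaged over start dates, against a margin of 15. The documents give no reason to think that the non-inferiority conclusion would change. The reason to act is that the primary outcome can be made complete for every child seen in window at almost no cost.

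The result assumes that treatment runs to the 12-week maximum and that completion means that date. If an earlier stop counted as completion, the window would close sooner and the gap would shrink. The effect on the rate also assumes a constant hazard.

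**What to change.** In the Section 6.1 visit table and the visit 8 text, let visit 8 open no earlier than 12 weeks + 24 months after day 1. One form is 27 months -5/+14 days. The nominal date is never less than 5 days after closing, so this leaves no shortfall for any start date under either counting convention. Count only events up to the closing date, so that later visits add no time at risk.

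State in Section 2.1 whether relapse onset or start of treatment must lie inside the window. If a relapse is ongoing and untreated at visit 8, record its later treatment status by a brief follow-up contact.

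The cost is slightly tighter scheduling (20 permitted days instead of 29) and an occasional telephone call. The latest permitted date does not move, so last subject out and the sample size stay as planned.

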2.2 Secondary Objectives and Secondary Endpoints

Secondary endpoints are divided into five items:

- 1. Course of the disease as described by the following criteria
 - a. Time from remission to first relapse
 - b. Number of relapses during follow-up
 - c. Mean relapse rate per patient and year
 - d. Number of frequent relapsers
 - e. Time from remission to intensification of immunosuppressive treatment with other drugs due to glucocorticoid-induced toxicity
 - f. Rate of patients who require more intense immunosuppressive treatment
- 2. Glucocorticoid-associated toxicity:
 - a. Cumulative prednisone dose as mg/m²
 - b. As there is no validated score for glucocorticoid-induced toxicity, each item is registered separately. At visits 1-8, body mass index, arterial hypertension, and growth failure will be checked for quantitative influence, striae, hypertrichosis, acne, and psychological disturbances by yes or no for qualitative influence. Additionally, at visits 1, 5, and 8, patients will be checked for cataract and glaucoma (by yes or no).

.....

- 3. Mycophenolate mofetil-associated toxicity: At all visits, patients will be checked for known side effects of MMF, especially diarrhea, blood cell count disturbance, and infections.
- 4. Health-related quality of life, which is impaired in children with nephrotic syndrome [21], will be measured with a validated questionnaire (DISABKIDS) at visits 1/5/8.
- 5. Days missing school attendance and days of hospitalization will be documented as a measure for the impact of the disease on everyday life.

It is expected that MMF-based regimen will avoid acute and long-term glucocorticoid-associated toxicity and is therefore superior regarding the benefit/risk ratio. However, this will not be tested confirmatorily since there exists no endpoint/score summarizing the different aspects of side effects.

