3 STUDY DESIGN AND DESCRIPTION

3.1 Study design

This is a prospective, randomized, multicenter, controlled, open, parallel group phase III study.

After initiation of the study, patients will be screened consecutively and eligible patients will be enrolled into the study at each center. To achieve comparable intervention groups and to minimize a potential selection bias, patients will be allocated in a concealed fashion by means of randomization using a centralized web-based tool (www.randomizer.at).

Each sites' principal investigator has to declare to the coordinating investigator/sponsor that he/she will conduct the study according to the protocol, ethical rules, and to provide the support as needed. To minimize a potential performance bias, this will be fixed in a contract prior to commencing the study. The clinical monitor will introduce the sites in detail to study procedures and documentation in advance.

Bias by potential influential factors will be addressed by inclusion as covariates into the statistical analysis. Independent clinical on-site monitoring to ensure patients safety and integrity of the clinical data in adherence to study protocol will focus on source data documentation, correctness of data, and adherence to study procedures, e.g. randomization and treatment.

Based on the performed interventions and planned analysis blinding is not feasible to minimize a detection bias, because the interventions can easily be differentiated due to visible side effects such as obesity, which is only expected in the control group. Furthermore, MMF is used in liquid form and prednisone as a tablet. The primary endpoint is based on standardized diagnostic work-up results, i.e. is an objective criteria.

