The blood test contains: blood cell count (leukocytes, erythrocytes, hemoglobin, and thrombocytes), HbA_{1c} , creatinine, blood urea/blood urea nitrogen (BUN), uric acid, calcium, phosphate, alkaline phosphatase, 25-OH Vitamin D, total protein, albumin, GPT/ALT, IgG, IgE, Cholesterol.

Study specific investigations are:

- 24 h ambulatory blood pressure measurement (24h-ABPM) performed by the study center with documentation of the median of systolic blood pressure (day), of the median of diastolic blood pressure (day), the median of systolic blood pressure (night), the median of diastolic blood pressure (night).
- o **Ophthalmologic investigation** performed by any ophthalmologist will document cataract (yes/no) and glaucoma (yes/no)
- O Health related quality of life (HRQoL) DISABKIDS as standardized questionnaires to assess health related quality of life is used. There exists a parental questionnaire, a questionnaire for children aged ≥8 years and one for children aged 4-7 years of age. Children below 4 years of age will not receive a questionnaire.
- Echocardiography (Echocardio.) is optional for the INTENT study and will be performed by a pediatric cardiologist. The documented parameters are: LVID (left ventricular internal diastolic diameter), LVIS (left ventricular internal systolic diameter), PWT (posterior wall thickness), and IVST (interventricular septic thickness). The LVID index, the LV FS (Left ventricular fractional shortening), LVM (left ventricular mass), LVM index, and LVH (Left ventricular hypertrophy) are computed.

These study specific investigations can be performed in a time frame of -21 days/ +7 days around the visit date.

The persons having care and custody of the child and the patient will be informed about the randomized medication, especially its handling, dosing, intake in relation to food intake and storage (see 5.4.2).

Further, the use of the patients´ diary is explained. Daily dip stick (Albustix®), given medication (if control intervention: dosage of prednisone in mg; if experimental intervention: dosage of MMF in ml and dosage of prednisone in mg), as well as days of missing school, infections, hospitalization, or other events the persons having care and custody of the child feel important to document.

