The blood test contains: blood cell count (leukocytes, erythrocytes, hemoglobin, and thrombocytes), HbA_{1c}, creatinine, blood urea/blood urea nitrogen (BUN), uric acid, calcium, phosphate, alkaline phosphatase, 25-OH Vitamin D, total protein, albumin, GPT/ALT, IgG, IgE, Cholesterol

Study specific investigations are:

- 24 h ambulatory blood pressure measurement (24h-ABPM) performed by the study center with documentation of the median of systolic blood pressure (day), of the median of diastolic blood pressure (day), the median of systolic blood pressure (night), the median of diastolic blood pressure (night).
- Ophthalmologic investigation performed by any ophthalmologist will document (Cataract (yes/no) and Glaucoma (yes/no))
- Health related quality of life (HRQoL) DISABKIDS as standardized questionnaires to assess health related quality of life is used. There exists a parental questionnaire, a questionnaire for children aged ≥8 years and one for children aged 4-7 years of age. Children below 4 years of age will not receive a questionnaire.

Echocardiography (Echocardio.) is optional for the INTENT study and will be performed by a pediatric cardiologist. The documented parameters are: LVID (left ventricular internal diastolic diameter), LVIS (left ventricular internal systolic diameter), PWT (posterior wall thickness), and IVST (interventricular septic thickness). The LVID index, the LV FS (Left ventricular fractional shortening), LVM (left ventricular mass), LVM index, and LVH (Left ventricular hypertrophy) are computed.

These study specific investigations can be performed in a time frame of ±28 days around the visit date.

Visit 6

Visit 6 is scheduled at 15 months (± 14 days) after day 1 (= first day of treatment with standard therapy for first episode of idiopathic nephrotic syndrome in children).

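### At visits 5 and 8, cataract and glaucoma are judged by an ophthalmologist from whom nothing in the protocol withholds the treatment arm

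*Protocol*

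**What the plan says.** Section 3.1 describes an open trial and gives two reasons. The first is that "blinding is not feasible to minimize a detection bias, because the interventions can easily be differentiated due to visible side effects such as obesity"; the second is that "MMF is used in liquid form and prednisone as a tablet". It then adds one reassurance: "The primary endpoint is based on standardized diagnostic work-up results, i.e. is an objective criteria". Masking of outcome assessors is not discussed there or elsewhere in the protocol.

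Section 2.2 lists cataract and glaucoma among the glucocorticoid toxicity items: "at visits 1, 5, and 8, patients will be checked for cataract and glaucoma (by yes or no"). The synopsis names both under its key secondary endpoints.

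Section 6.1 says who examines. At visit 1 the examination is "performed by any ophthalmologist will document cataract (yes/no) and glaucoma (yes/no"). At visits 5 and 8 it is "performed by any ophthalmologist will document (Cataract (yes/no) and Glaucoma (yes/no")). In the same lists, ambulatory blood pressure measurement is assigned to the study center; the eye examination is not.

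Section 8.4 makes all secondary outcomes descriptive, with descriptive p-values and 95% confidence intervals. Section 2.2 expects an advantage in benefit/risk from lower glucocorticoid toxicity and says that this will not be tested confirmatorily.

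**The concern.** Section 3.1 treats blinding as all or nothing. Keeping families and treating staff unaware of a liquid versus a tablet is one question; keeping a separate examiner unaware of the arm is another, and the protocol does not address it. The objectivity argument does not cover the eye findings, which are yes/no judgements with no diagnostic criterion or grading stated in the protocol.

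An examiner who knows that a child had the full prednisone course may look harder for, or call more readily, the lens and pressure changes linked to steroids. Such an over-call would favor the toxicity advantage that the sponsor expects. Sections 1.2 and 1.3 rest the case for the new regimen on less glucocorticoid toxicity at comparable efficacy, so these endpoints belong to the benefit side of that case. Who knows the arm at the examination is settled during conduct; no later analysis can restore masking.

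**Working it through.** The protocol gives no figure on this point. The sample size does not depend on it: the Farrington-Manning calculation with 51% in both arms, margin 0.15, one-sided 5% and 80% power gives 135.3, so 136 per group and 272 in total, and 272 / 0.80 = 340. Masking an eye examiner changes none of these inputs. The rest is a comparison of sections.

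**1. Does each reason against blinding reach the ophthalmologist?**
- Formulation (3.1): no. The eye examiner neither dispenses nor gives study drug.
- Visible side effects (3.1): in part. Anyone who sees the child can see weight gain or a cushingoid face.
- Objectivity (3.1): claimed for the primary endpoint only.

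**2. Which examinations can carry a between-arm bias?**
- Visit 1 is the randomization visit, 0 to 5 days after remission. Its eye examination may take place from 21 days before to 7 days after the visit. It is a baseline, may precede allocation, and at the latest falls 7 days after it.
- Visit 5 is 9 months after day 1 and visit 8 is 27 months after day 1. Each visit has a window of ±14 days, and the eye examination a further ±28 days.
- Initial treatment ends 12 weeks after day 1 (5.4.2). Nine months is 9 × 52/12 = 39 weeks, and 39 − 12 = 27 weeks after treatment. With both windows at their earliest, 27 − 2 − 4 = 21 weeks.
- Visit 8: 27 × 52/12 = 117 weeks; 117 − 12 = 105 weeks after treatment, at the earliest 105 − 6 = 99 weeks.

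So visits 5 and 8 are where the arm could color the finding, and both fall well after study treatment has stopped.

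**3. How well do visible signs identify the arm by then?**
- Every child had daily glucocorticoids to reach remission (4.2), and the MMF arm also received alternate-day prednisone for two weeks after randomization (5.4.2).
- Section 8.1 assumes treated relapse in 51% of each arm within 24 months after initial treatment: 0.51 × 170 = 86.7, about 87 children per arm. Standard relapse treatment is prednisone (Appendix 1).
- By visit 8, on the protocol's own assumption, about half of each arm will have had at least one further prednisone course. The protocol gives no corresponding figure for visit 5.

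Steroid signs are therefore an imperfect guide to the arm at these visits. A referral saying that the child has received glucocorticoids is true in both arms.

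**4. Is withholding information foreign to this trial?** No. Centers are not told the mycophenolic acid results (6.1, visits 2 and 3), and those preparing the SAP see only blinded data (8.4).

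**5. Size.** A magnitude would need the true rates of cataract and glaucoma and the extra false positives caused by knowing the arm. The documents give neither, so no estimate is offered.

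**The case against.** The best reply is that the first reason in 3.1 does apply to an eye examiner. Steroid effects are visible, section 1.1 says that not all are reversible, and it cites one study in which excess weight gain persisted in 47% of patients after treatment. Families know the arm and may mention it. This stands: masking would be partial, and a reader who took it to be complete or free of cost would go beyond the documents.

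Nor does the protocol say that the examiner is told the arm, or that the examiner comes from outside the center. The text leaves the choice of ophthalmologist open and is silent on disclosure. The point is only that nothing prevents disclosure.

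Three wider readings are tempting and should not be drawn:
- That visit 1 is equally exposed. It is a baseline and may precede randomization.
- That echocardiography has the same weakness. It is optional, records measured dimensions and computed indices, and is not among the secondary endpoints in 2.2.
- That a false rate ratio can be attached to the bias. Any such number would only restate the assumed rates, and it would suppose over-calling confined to one arm although many children in both will have had repeat steroid courses.

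It is also fair that striae, acne, hypertrichosis and psychological disturbances are yes/no items recorded openly at study visits. Masking the eye examiner protects two items of the toxicity profile, not all of it. That limits the gain without removing it.

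**Conclusion.** The point holds in a limited form. The protocol dismisses blinding for the trial as a whole without considering a masked assessor, and it leaves two yes/no secondary endpoints at visits 5 and 8 open to detection bias that could be lowered with little effort. This rests on two readings of the text: that the examiner need not belong to the treating team, and that no instruction withholds the arm. The size is unknown, and the direction, toward the expected toxicity advantage, is plausible but not shown.

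A reader might infer that the non-inferiority conclusion is at risk. It is not: the primary endpoint is relapse, the eye findings are descriptive, and the toxicity advantage is expressly not tested confirmatorily. This is a cheap improvement.

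**What to change.** In section 3.1, and at visits 5 and 8 in section 6.1:
- state that the ophthalmologist is not told the allocated arm;
- use a standard referral saying only that the child has nephrotic syndrome and has received glucocorticoids;
- ask families not to name the arm at the examination;
- have the examiner record whether the arm became known.

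The cost is one referral form, a short addition to the site instructions and one extra item to record. No staff, procedure or patients are added, and 340 randomized stays as planned. The downside is that masking is partial: some families will disclose the arm and persisting steroid signs may unmask some children. The recorded item lets the report say how often the arm became known.
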